16. TRIAL INSURANCE AND INDEMNITY

16.1 Negligent Harm

The usual NHS indemnity arrangements for negligent harm will apply.

16.2 Research Liabilities

The sponsor (University of Nottingham) has third-party liability insurance cover in accordance with all local legal requirements.

As a precautionary measure, the investigator, the persons instructed by him and the hospital are included in such cover in respect of work done by them in carrying out this study to the extent that the claims are not covered by their own professional indemnity insurance.

In addition, the study engineers will carry their own 3rd party liability insurance should the installation of the water softening devices result in flood or damage to property.

16.3 Non negligent harm

The devices to be used in the study will be covered by product warranty. Other than this, no compensation exists for non-negligent harm.

17. PUBLICATION POLICY

During the period of the trial, press releases will be issued from the Centre of Evidence Based Dermatology and will be approved by either the Chief Investigator ([name]) or the Lead Applicant ([name]). No party will be entitled to submit any publicity material without prior approval from the co-ordinating centre.

Trial publications and conference presentations will be submitted to the HTA for approval prior to submission to the event organisers or the editors. All publications will acknowledge the support of the HTA in funding this trial, and the support of the water industry.

Neutral or negative results will not constitute a reasonable justification to delay publication.

DFI Dematitis Family Impact

HTA Health Technology Assessment

ITT Intention To Treat

NIHR National Institute for Health Research POEM Patient Oriented Eczema Measure

QALY Quality Adjusted Life Years

SASSAD Six Area Six Sign Atopic Dermatitis Score

SWET Softened Water Eczema Trial
TCW Totally Controlled Weeks
TMG Trial Management Group
TSC Trial Steering Commitee
WCW Well Controlled Weeks

1. INTRODUCTION

This analysis plan details the planned statistical analyses for the Softened Water Eczema Trial (SWET).

This is a single-blind, parallel group, randomised controlled trial of 12-week duration, followed by a 4-week cross-over period. The objective is to assess whether the installation of an ion-exchange water softener improves eczema in children, and if so to establish the likely cost and cost-effectiveness of the intervention.

Participants are randomised to one of two groups on a 1:1 basis. The first group have a water softener installed the first 12 weeks of the trial followed by a 4 week washout period. The second group, the delayed treatment group, have the water softener installed for four weeks from week 12 onwards.

| | STUDY PERIOD = 16 weeks | |
|---------|--|----------------|
| | 0 to 12 weeks | 12 to 16 weeks |
| Group A | Usual eczema care + water softener installed (n = 155) | Unit removed |
| Group B | Usual eczema care + delayed installation (n = 155) | Unit installed |

Throughout this document Group A will be referred to as the immediate installation group, and Group B as the delayed treatment group.

The analyses described in this document will be performed by the designated statistician at the MRC Clinical Trials Unit. All data will be analysed using Stata Version 10.1.

2. TRIAL OBJECTIVES

There are two key objectives for the trial:

- 1. To assess whether the installation of an ion-exchange water softener improves eczema in children
- 2. If so, to establish the likely cost and cost-effectiveness of this intervention

3. ENDPOINTS

Due to the nature of the intervention this study is being conducted as a single blind trial. For this reason objective, and validated outcome measures have been used (Schmitt, 2007).

3.1. Primary Endpoint

Participants with moderate to severe eczema will be randomised to one of the two groups described previously.

The primary endpoint is the difference between the immediate installation and delayed intervention groups with regard to mean change in disease severity (Six Area Six Sign Atopic Dermatitis Score – SASSAD) at 12 weeks compared to baseline.

3.2. Secondary Endpoints

- 1. The difference between baseline and week 12 of the proportion of time spent moving during the night. Movement will be captured for periods of one week at weeks 1 and 12, and will be measured using accelerometers (Actiwatch). These units are worn by the child in the same way as a wrist watch. Due to possible differences between the units every effort was made to ensure the children always used the same unit and where this was not the case this has been documented. A sensitivity analysis will be performed excluding those who did not use the same unit throughout the trial.
- 2. Difference in the proportion of children who report either a good or excellent improvement in eczema severity at 12 weeks (using a 5-point Likert scale). As these data were not collected¹, responders will be grouped into three groups; those who report a reasonable (≤20%), good (>20% and ≤50%) or excellent (>50%) improvement in SASSAD score at 12 weeks.
- 3. Amount of topical corticosteroid / calcineurin inhibitors used during the 12 week study period. This information is captured by weighing the medication at each visit and then summarised according to steroid strength to give the total amount used from baseline to week 12. Nurses will also be providing an indication of the level of accuracy of any estimates. A sensitivity analysis will be performed excluding those for whom the nurse is not confident about the amount of medication used.
- 4. Difference in Patient Oriented Eczema Measure (POEM). This scale is a well validated tool that has been developed to capture symptoms of importance to patients (rather than objective signs that are used in traditional severity scales, such as SASSAD).
- 5. Difference in the number of totally controlled weeks (TCW) and well-controlled weeks (WCW) based on the number of days with eczema symptoms and the number of days that topical treatment is applied up to primary endpoint at 12 weeks. This will be derived from the symptom diaries.
- 6. Difference in the mean change from baseline in the Dermatitis Family Impact (DFI) questionnaire at 12 weeks.

-

Omitted from CRFs to avoid unblinding of research nurses, and also on reflection this measure would be too open to bias in a single-blind study. Therefore improvement based on improvement in SASSAD score is preferable.

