| Water Engineer Home screening visit Home visit to assess suitability of residence for installation of softener Estimate salt requirements and assess availability of storage for salt supply Test water hardness | Research Nurse Recruitment Visit clinic appointment Baseline characteristics Eligibility criteria checked SASSAD POEM Utility measures (DFI and EQ-5D) Weigh medications UTP questionnaire Digital photo of index site Saliva sample Explanation and issue of Diary 1 Explanation of accelerometer (Actiwatch TM) Issue Water Softener Information sheet Randomisation | Water Engineer At 0–2 weeks ♦ Install unit (Group A) within 10 working days of DAY ZERO (date of recruitment visit) ♦ Advice given to reduce soap consumption etc. ♦ Issue water sampling containers + prepaid envelopes | Research Nurse Clinic appointment At 4–6 weeks ◇ SASSAD ◇ POEM ◇ Digital photo of index site ◇ Saliva sample (if not obtained at baseline) ◇ Collection of week 1 Actiwatch™ data ◇ Weigh medications ◇ Collection of Diary 1 and Issue of new Diary 2 | Trial Manager At 8 to 9 weeks | Research Nurse Clinic appointment At 12–14 weeks SASSAD POEM Utility measures Digital photo of index site Weigh medications Collection of Week 11-12 Actiwatch™ data and Actiwatch™ Collection of Diaries 2 Issue Diary 3 Explanation of cross-over phase | Water Engineer At 12–14 weeks ◇ Remove unit (Group A) within 10 working days of 12 week anniversary of installation ◇ Install unit (Group B) within 10 working days of 12 week appointment with RN; retest water hardness. ◇ Advice given to reduce soap consumption etc (Group B) ◇ Issue water sampling containers and pre-paid envelopes (Group B) | Research Nurse Water Engineer At 16 to 18 weeks Clinic appointment with Research Nurse to carry out: SASSAD POEM Utility measure Collection of Diary 3 Visit by Water Engineer to: Remove unit (Group B), if they do not wish to purchase unit, within 10 working days of 4 week anniversary of installation Reinstall unit (Group A) if they wish to purchase unit at first convenient time after 16 week appointment with RN. |

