8. DATA HANDLING

8.1. Missing data

The primary outcome is collected by nurses at study visits so missing items are not expected. Other missing data items such as age, sex, etc. will be queried so that there are no missing data for these variables.

Missing baseline water hardness score will be replaced with published water hardness data for that postcode.

For each endpoint the number with a missing outcome for each treatment group will be reported with reasons given where available.

If less than 5% of data are missing for the primary endpoint only participants with complete data will be included in the full ITT primary analysis. An additional sensitivity analysis will be conducted replacing missing data with the maximum value at baseline and week 4 (where this exists). If more than 5% of data are missing for the primary endpoint then more complex multiple imputation techniques will be used to handle the missing values. Secondary endpoint analyses will be analysed using a complete case analysis as these are only considered supportive of the primary endpoint analysis.

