10.2. Secondary Efficacy Analyses

- 1) The difference between baseline and week 12 of the proportion of time spent moving during the night will be compared across intervention groups using a t-test. The average of the first three nights of evaluable data at week 0, and the last three nights at week 12 will be used.
- 2) The proportion of children who report a reasonable (≤20%), good (>20% and ≤50%) or excellent (>50%) improvement in SASSAD score at 12 weeks, will be compared using a chi-squared test.
- 3) Amount of topical corticosteroid / calcineurin inhibitors used during the 12 week study period. This will be captured by weighing the medication at each visit. This will then be summarised by the nurses at week 12, including a measure of the degree of accuracy of any estimates. These will be spilt into two groups, low strength consisting of mild and moderate topical steroids, and high strength consisting of potent and very potent topical steroids and mild and moderate calcineurin inhibitors. The difference in the amount (in grams) of each of the two groups will be assessed using t-tests.
- 4) The difference in the change from baseline to week 4 and baseline to week 12 Patient Oriented Eczema Measure (POEM) scores will be compared using t-tests.
- 5) Difference in the number of well controlled weeks (WCW) as defined in section 8.3, will be analysed using a t-test. The number of totally controlled weeks (which are a subset of the WCW), will also be summarised.
- 6) Difference in the mean change from baseline in the Dermatitis Family Impact (DFI) questionnaire at 12 weeks, will be analysed using a t-test.

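### Total grams of topical treatment are compared although the closing weighing may fall at 12 to 14 weeks, and well-controlled weeks have no rule for partial diaries (minor)

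*Combined protocol and SAP*

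**What the plan says.** - **Grams.** SAP 3.2 item 3 names the endpoint as "Amount of topical corticosteroid / calcineurin inhibitors used during the 12 week study period", weighed at each visit and summed "to give the total amount used from baseline to week 12". SAP 10.2 item 3 splits treatments into low and high strength and adds: "The difference in the amount (in grams) of each of the two groups will be assessed using t-tests". The one sensitivity analysis drops children for whom the nurse doubts the amount. It addresses weighing accuracy, not time observed.
- **Timing.** The protocol's Table 1 entry for the closing visit reads "Clinic appointment At 12–14 weeks SASSAD POEM Utility measures Digital photo of index site Weigh medications". Day zero is the recruitment visit, and the window is the same for both arms. Only Group A has a unit fitted at the start, at 0–2 weeks and within 10 working days of day zero (protocol 5.5 and 9.5 call this the ideal). Table 1 ties removal of that unit to the 12-week anniversary of its installation.
- **Controlled weeks.** SAP 3.2 item 5 stops the count at 12 weeks: it uses days with symptoms and "the number of days that topical treatment is applied up to primary endpoint at 12 weeks". SAP 10.2 item 5 says: "Difference in the number of well controlled weeks (WCW) as defined in section 8.3, will be analysed using a t-test". Totally controlled weeks (TCW) are only summarised in the SAP, whereas protocol 10.4 tests both. SAP 8.3 defines each kind of week by a ceiling on bad days. It does not say how a blank day is scored, how many recorded days make a week usable, or what the denominator is.
- **Missing data.** SAP 8.1 states: "Secondary endpoint analyses will be analysed using a complete case analysis". It does not say when a diary counts as complete. SAP 9.3 has diaries collected at withdrawal, so partial diaries are foreseen.

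**The concern.** Total grams are weekly use multiplied by weeks observed. Two children with the same weekly use have different totals if one is weighed at week 12 and the other at week 14. If one arm is on average weighed later, the t-test cannot separate longer observation from heavier use. Later weighing in Group A would mask a saving in topical treatment; later weighing in Group B would create one.

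This matters because protocol 8.3 lists use of topical therapy among the objective secondary outcomes, in a trial where families know their allocation.

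For well-controlled weeks (WCW) the question is what happens to weeks without a complete record. SAP 8.3 settles the equivalent question for the accelerometers, with limits on usable nights and a minimum of three. It does not do so for the diaries.

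**Working it through.** **1. The plan's own figure.** The documents give no size or variability for grams or WCW. The stated sample size rests on SASSAD: difference 20% × 20 = 4 points, SD 10, power 90%, 5% significance (taken as two-sided), attrition 15% (SAP 4). Per arm, 2 × (1.960 + 1.282)² × 10² / 4² = 131.4, so 132. In total 264, and 264 / 0.85 = 310.6, so 311 against the stated 310: reproduced. The steps on grams use 132 per arm.

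**2. Width of the window.** 14/12 − 1 = 16.7%.

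**3. Same timing in both arms.** Assume visits spread uniformly over 12–14 weeks: mean 13, variance 2²/12 = 0.333, squared coefficient of variation (CV) 0.333/13² = 0.00197. Let c be the CV of weekly use between children, independent of timing. Relative to no variation in timing, the variance of total grams is multiplied by [(1 + c²)(1 + 0.00197) − 1] / c²:

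- c = 0.5: 1.0099
- c = 1.0: 1.0039
- c = 1.5: 1.0028

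The cost is 0.3–1.0% in variance, and the false-positive rate stays at 5%.

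**4. Mean timing differs by d weeks, true weekly use equal.** The relative shift is s = d/12. Its standard error is c × √(2/132) = 0.123c. A two-sided 5% test rejects with probability Φ(−1.96 − s/SE) + Φ(−1.96 + s/SE).

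| Mean difference d (assumed) | Shift in grams | False positives, CV 0.5 | CV 1.0 | CV 1.5 |
|---|---|---|---|---|
| 0 | 0% | 5% | 5% | 5% |
| 0.5 week | 4.2% | 10% | 6% | 6% |
| 1 week | 8.3% | 27% | 10% | 7% |
| 2 weeks | 16.7% | 77% | 27% | 15% |

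The last row is the extreme, with every child in one arm seen at week 12 and every child in the other at week 14.

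**5. After standardising.** If use is proportional to time, grams divided by weeks observed gives weekly use, and the shift is zero for any d.

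**6. WCW: why the direction is open.** Assume an average chance of one half that a week is well controlled, and a partial diary covering 6 of 12 weeks. A full diary is then expected to show 12 × 0.5 = 6 controlled weeks. For the half-length diary:

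- if unrecorded weeks add nothing: 6 × 0.5 = 3;
- if blank days are read as days without trouble: 3 + 6 = 9.

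With half-length diaries in 10% of one arm and 20% of the other (assumed), the arm means are 6 − 0.10 × 3 = 5.7 and 6 − 0.20 × 3 = 5.4 on the first reading. On the second they are 6 + 0.10 × 3 = 6.3 and 6 + 0.20 × 3 = 6.6. The spurious difference is 0.3 week either way, with opposite sign.

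A simulation of the first reading (155 per arm, 5,000 runs, weekly chance of control uniform between 0 and 1) gave 10.6% false positives. With 15% half-length diaries in both arms it gave 5.4%. Analysing the proportion of recorded weeks gave 4.6% and 5.0% respectively.

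**The case against.** The strongest reply is that nothing shows the arms differ. Both share one 12–14 week window from the same day zero, and the nurses who carry out the visits are blinded. The installation anniversary governs the engineer's removal of the unit, not the weighing. On equal timing the cost is trivial, as step 3 shows. Both outcomes are declared supportive in SAP 5, and WCW is already limited to 12 weeks. All of this stands.

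It rules out two stronger readings that a reader might infer:

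- **That the plan does turn unequal observation time into a treatment effect.** That needs a difference in timing between arms, which no section states. The documents only leave room for one. Group A alone waits for installation, and its families bypass the unit straight after the 12-week visit (protocol 9.5), so a full 12 weeks of exposure would call for a later visit. That is inference, not a stated schedule.
- **That a missing diary week always lowers the count.** SAP 8.3 defines control by few or no bad days, so a blank day read literally adds no bad day and could raise it.

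A proportion of recorded weeks also has limits. It gives a child with two diary weeks the same weight as one with twelve, and it stays biased if families stop recording because of the state of the eczema. This is why a definition of an evaluable week must come first, and why the proportion may serve as a sensitivity analysis.

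The reply does not remove the gap itself: there is no rate, no cut-off at day 84 for grams, and no partial-diary rule.

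**Conclusion.** The point holds as a minor one. Total grams are compared over a period that may differ between children by up to 16.7%, without standardisation. With equal timing in both arms the consequence is slight noise. With unequal timing it is a bias of about 4%, 8% or 17% for a mean difference of 0.5, 1 or 2 weeks. Those differences, the uniform timing and the CVs are assumptions; the documents give none of them.

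For WCW the visit window is not the issue. The missing rule for partial diaries is, and neither the size nor the direction of its effect can be known from the documents. The test at issue is the one on WCW, since the SAP only summarises TCW. Primary inference and the sample size of 310 do not depend on either outcome.

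**What to change.** - **SAP 3.2 item 3 and 10.2 item 3.** Analyse grams per week, separately for low and high strength: total grams divided by the days between the baseline and final weighings, times 7. Keep the t-test. Report days observed by arm.
- **SAP 8.3.** Define an evaluable diary week: how many recorded days it needs and how a blank day is treated.
- **SAP 10.2 item 5.** Analyse WCW as the proportion of evaluable weeks within days 1–84 (12 × 7), at least as a sensitivity analysis beside the count. Report evaluable weeks by arm, and summarise TCW on the same basis.
- **SAP 8.1.** State what a complete case means for a diary outcome.

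The cost is a few sentences in the SAP and derived variables from visit dates and diary entries. It needs no new data, no extra visits and no change to the sample size. The wording should be settled before the allocation codes are linked to the data.

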3.3. Tertiary Endpoints

If a beneficial effect is found the following tertiary analyses will be performed.

- 1) Speed of onset of benefit will be analysed in three ways. Firstly, the difference in the mean change in disease severity (SASSAD) at 4 weeks compared to baseline. Secondly, the final 4 week period (weeks 12 to 16) will be examined for the delayed treatment group. Finally the daily bother scores will be examined for the first 4 weeks of the trial for both groups.
- 2) Likely carry over effect will be examined using the full 16 week trial period for the immediate installation group. This information will be useful in planning the design of future trials in this area.
- 3) Predictors of response model, including baseline factors (see section 6.2)

4. SAMPLE SIZE

Sample size estimates are based on other published data relating to the use of SASSAD in patients recruited in secondary care. Based on a minimum clinically relevant difference of 20% in the change in SASSAD score between the 2 groups, and assuming a mean baseline SASSAD score of 20 with a standard deviation in change scores of 10, a sample size of 310 children will provide 90% power, with a significance level of 5% allowing for an attrition rate of 15%.

5. ITT ANALYSIS AND MULTIPLICITY

The SWET trial will be analysed as intent-to-treat (ITT) at week 12.

The ITT population will consist of all randomised participants with evaluable data. This will be the primary population used for the main analysis, which will use the randomised treatment allocation rather than actual treatment received. An additional sensitivity analysis will be performed excluding outliers.

Primary inference will be based on the primary endpoint analysis of the ITT population. Significance will be at the 5% level.

A secondary, per protocol analysis of the primary endpoint will be performed excluding the following participants:

- Those who were randomised into the study, but who failed to receive their allocated treatment.
- Those who are deemed to be major protocol violators as determined by the Protocol Violators Group (including independent members) review of the protocol deviation log.

Criteria for protocol violators are as follows:

- Missing SASSAD score at week 12
- Group A: exposed to fully softened water for <75% of the time their home has an active water softener in place (i.e. sleeping at home + unit fully working for <75% of the time their home has an installation)

- Group A: Participant away from home or with partially functioning water softener of >2 days/week for each of the 4 weeks prior to the primary outcome measure
- Group B: Participant away from home for > 2 days/week for each of the 4 weeks prior to the primary outcome measure
- Unblinding of research nurse prior to primary outcome measurement
- Starting new treatment prior to primary outcome measurement will be examined on a case-by-case basis to determine if they comprise a protocol violator.

Baseline characteristics (as described in section 6.2) will be summarised and if any major imbalance exists the analyses will be adjusted to account for this.

Analyses of all secondary endpoints and adjusted analyses will be considered supportive to the primary analysis so no adjustments for multiple comparisons will be made.

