10. STATISTICS

10.1 Statistical design

Analyses have been planned in order to place emphasis on objective outcomes that are less likely to be influenced by the potential bias inherent in a single-blind study. Nevertheless, a variety of additional tools are to be used that reflect more closely the disease process throughout the study period. Some of these are relatively objective indicators of disease activity (such as nocturnal movement and treatment application), whilst others reflect subjective concepts (such as self-reported symptoms in the POEM), in order to capture the many health-related dimensions affected by eczema.

The planned analyses should answer the following questions:

- 1. Does exposure to softened water for 12 weeks improve the symptoms and severity of eczema, compared to standard care?
- 2. Does softened water improve quality of life for patients and their carers?
- 3. Are water softeners a cost-effective treatment for children with atopic eczema?

In addition, tertiary analyses will explore the following parameters:

4. How quickly the benefits of softened water become evident.

5. How quickly the benefits of softened water are lost once treatment is stopped.

The main intention-to-treat analysis will be conducted at 12 weeks. An additional per protocol analysis will also be conducted for the primary outcome in order to test the proof of concept.

A sub-group analysis will also be conducted based on the presence or absence of mutations on the gene filaggrin (*see* section 12). Mutations on the filaggrin gene have been associated with dry skin and may therefore be a useful predictor of treatment response.

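### The per-protocol criteria count whole-period absence in one arm only, and can keep a less exposed child while removing a more exposed one, which puts the secondary proof-of-concept analysis at risk

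*Combined protocol and SAP*

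**What the plan says.** Protocol section 10.1 gives the analysis its purpose: "An additional per protocol analysis will also be conducted for the primary outcome in order to test the proof of concept". SAP section 5 makes it secondary ("A secondary, per protocol analysis of the primary endpoint will be performed excluding the following participants") and states that "Primary inference will be based on the primary endpoint analysis of the ITT population".

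Two kinds of participant leave the per-protocol set. The first is "Those who were randomised into the study, but who failed to receive their allocated treatment". The second is anyone whom a review group with independent members deems a major violator. The criteria listed for that group that concern exposure or absence are:

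- Whole period, Group A only: "Group A: exposed to fully softened water for <75% of the time their home has an active water softener in place", explained as "sleeping at home + unit fully working for <75% of the time their home has an installation".
- Last four weeks, Group A, counted back from the week-12 SASSAD: "Group A: Participant away from home or with partially functioning water softener of >2 days/week for each of the 4 weeks prior".
- Last four weeks, Group B: "Group B: Participant away from home for > 2 days/week for each of the 4 weeks prior to the primary outcome measure".

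Group B has no whole-period criterion. The list contains no latest installation date and no minimum number of exposed nights. Protocol section 5.5 and SAP section 9.2 both name absence from home as the adherence or compliance measure, and neither limits it to one arm.

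**The concern.** A per-protocol comparison already departs from randomisation. To be informative, it should at least select children in the two arms on the same behaviour wherever that behaviour can occur in both, and its exposure rule should rank children by exposure. The listed criteria fall short on both counts. Long absence can occur in either arm, but over the whole period it counts only in Group A. The last-four-weeks test and the time-installed denominator can also keep a child with little softened water and remove one with more.

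One-sided removal risks selection bias. Retaining poorly exposed Group A children risks diluting the effect that the analysis is meant to show. This matters most if the ITT result is null or marginal, because readers will then look to the proof-of-concept result.

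**Working it through.** **Stated figures.** The per-protocol rules give no sample size and no expected exclusion rate, so there is no figure of their own to reproduce. The nearest is the main sample size (SAP section 4). The target difference is 20% of 20 = 4 points with SD 10. At two-sided 5% and 90% power this needs 132 per arm, or 264, and 264/0.85 = 311, which agrees with 310. Only the 4-point target is used below, for scale.

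**Inputs.** The 75% threshold, the limit of more than 2 days a week and the four-week window come from SAP section 5. The base case has a unit in place for 84 days (12 weeks). A day away is taken as one night without exposure, and the unit otherwise works fully. Exposure = (days in place − days away) / days in place.

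**1. Same absence, different arm.** A child is away 7+7+7+2 = 23 of the last 28 days. The week with 2 days does not exceed 2, so the last-four-weeks rule is not met in either arm.
- Group A: (84 − 23)/84 = 61/84 = 72.6%, below 75%: removed.
- Group B: no further rule applies: kept, whatever the absence in earlier weeks.

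**2. Order of exposure within Group A.**

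| Days away, last 4 weeks | Overall exposure | Exposure in last 28 days | Result |
|---|---|---|---|
| 0+7+7+7 = 21 | 63/84 = 75.0% | 7/28 = 25.0% | kept |
| 3+3+3+3 = 12 | 72/84 = 85.7% | 16/28 = 57.1% | removed |

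The removed child has more exposure on both measures. Other installation times change the example but not the finding:
- 70 days in place: 17 days away (0+3+7+7) is kept at 53/70 = 75.7%; 3 days in each week is removed at 58/70 = 82.9%.
- 98 days in place: 23 days away (2+7+7+7) is kept at 75/98 = 76.5%; 3 days in each week is removed at 86/98 = 87.8%.

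Reading the rule as any one week instead of every week does not help. It would remove a child with a single 3-day absence (81/84 = 96.4%).

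**3. Denominator.** A unit fitted at week 8 is in place for 28 days before a day-84 visit. It passes with 0.75 × 28 = 21 nights, and 21/84 = 25.0% of the 12 weeks. The 7 nights lost cannot breach the last-four-weeks rule, which needs at least 3 in each week, or 12. A unit in place for only 14 days passes with 11 nights (0.75 × 14 = 10.5), and 11/84 = 13.1%.

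**4. Possible size, by assumption only.**
- If a share p of Group A is removed one-sidedly and their mean change differs by d from those who stay, the estimate shifts by p × d. The range runs from 2% × 2 = 0.04 points to 15% × 10 = 1.5 points, against a target of 4.
- If a share q of Group A is kept with exposure e and effect is proportional to exposure, a 4-point effect becomes 4 × (1 − q + qe). The range runs from 3.9 (q = 5%, e = 0.5) to 3.3 (q = 20%, e = 0.13).

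The documents support no particular values of p, d, q or e.

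**The case against.** The best reply is that these are constructed cases in a secondary analysis, with several safeguards around them.

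- **Some asymmetry is unavoidable.** Group B has no softener before week 12, so a unit-function rule cannot apply there, and the last-four-weeks absence rule is mirrored. This stands for unit function. It does not explain why absence over the whole period counts in one arm only.
- **Long absences should be rare.** Protocol section 7.2 excludes children planning more than 21 days away in 16 weeks, and aims to avoid planned holidays in the four weeks before the week-12 visit. The 23-day case therefore needs unplanned absence. The 21-day case does not exceed the entry limit, and the holiday provision is only an aim.
- **The examples depend on timing.** With 98 days in place, the 23-day child is kept in Group A too (76.5%). With 70 days, the 21-day child is removed (49/70 = 70%). Both are correct, but the misordering persists at all three durations.
- **Late installation may be caught.** A reader might infer that late fitting costs nothing. The documents do not support that. Protocol section 5.5 sets a target of 10 working days, and SAP section 9.2 has every deviation logged and classed as major or minor. A week-8 installation could be excluded by that route, but nothing listed requires it.
- **Time installed is a defensible denominator.** Protocol Table 1 allows Group A installation at 0–2 weeks. A child fitted at day 14, away 8 nights afterwards and seen at day 84, has 62/70 = 88.6% exposure. A fixed 84-night denominator would give 62/84 = 73.8% and wrongly remove that child. This objection stands and shapes the fix.
- **Refusal of the unit at week 12.** Read literally, the exclusion for not receiving allocated treatment could reach a Group B family that declines its unit after the primary outcome. That reading is strained, since the comparison up to week 12 is with usual care and the other timed criteria precede the outcome. A clarifying phrase is enough.

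**Conclusion.** The concern holds as a defect in the stated criteria. Whole-period absence can remove a child from Group A but never from Group B. The every-week test can reverse the order of exposure. The 75% rule alone sets no floor on exposure over the 12 weeks.

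A reader might go further and infer that the per-protocol result is biased, or cannot test proof of concept. The documents do not support that: they give no exclusion rates and no outcomes for the affected children, and the direction of any shift is open. The ranges of 0.04 to 1.5 points for one-sided removal, and 3.9 to 3.3 for a diluted 4-point effect, rest wholly on assumed shares. The supported conclusion is a risk of selection bias and dilution in a secondary analysis, with the primary ITT inference unaffected. The worked cases assume literal application of the listed criteria, before any discretion by the review group.

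**What to change.** Amend SAP section 5 before the allocation is revealed:

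1. Apply one whole-period home-presence criterion to both arms, from randomisation to the week-12 visit. Keep softener function as an additional Group A criterion.
2. Replace the every-week test with a total over the last 28 days in both arms, for example more than 8 days, which is the SAP's own 2 days a week × 4. Both children in the table (21 and 12 days) would then be removed, as would the 23-day child in either arm.
3. Keep time installed as the Group A exposure denominator, but list installation well outside the planned 0–2 week window as a violation. Children fitted on schedule are then not penalised.
4. State that failure to receive allocated treatment refers to events before the week-12 SASSAD.
5. Have the review group decide without sight of SASSAD. SAP section 9.2 places its review at the end of the trial, when outcomes exist, and the documents do not say that it is blind to them. Report exclusions by arm and reason.

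A complier-average estimate may be added as an optional sensitivity analysis with its assumptions stated. It should not be the preferred estimate: it still needs a definition of complier, and it assumes that allocation acts only through softened water, which is open to doubt when families know their arm.

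The cost is SAP wording. The diaries already record nights away (Protocol section 9.1.2), and Group A sends weekly water samples (Protocol sections 5.2 and 9.5). The downside is a few more exclusions, mainly in Group B.
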